8.1. Primary Outcome Analysis

Rectal mucosal IgG concentrations (GMT) against GC OMV antigens at days 1, 29, 43, 57, and 181 in each Treatment group are shown in [Table 14](#), [Figure 2](#), and [Figure 4](#). The summary of GMFR from baseline are also shown in [Table 14](#). The distributions of rectal mucosal IgG titers are graphically summarized using reverse cumulative frequency distributions in [Figure 36](#) and [Figure 37](#). All results are presented in [Listing 9](#). A summary of GMT and GMFR Rectal mucosal IgG by sex is shown in table [Table 15](#), [Figure 3](#), and [Figure 5](#).

8.2. Secondary Outcome Analyses

Serum IgG concentrations (GMT) against GC OMV antigens at days 1, 29, 43, 57, and 181 in each Treatment group are shown in [Table 16](#), [Figure 6](#) and [Figure 8](#). The summary of GMFR is also shown in [Table 16](#). The distributions of serum IgG titers are graphically summarized using reverse cumulative frequency distributions in [Figure 38](#) and [Figure 39](#). A summary of GMT and GMFR serum IgG by sex is shown in [Table 17](#), [Figure 7](#), and [Figure 9](#). Summaries of the ratio of serum to mucosal IgG concentration will be generated at each time point and presented in [Table 22](#) and [Table 23](#). All results are presented in [Listing 10](#).

8.3. Exploratory Outcome Analyses

For the exploratory outcomes, summaries of IgG antibody concentrations (GMT) at each time point and GMFR in each treatment group are shown in [Table 18](#), [Table 19](#), [Table 20](#), and [Table 21](#). Summaries of the ratio of serum to mucosal IgG GMT results will be presented in [Table 22](#) and [Table 23](#). Summaries of pairwise ratios of mucosal IgG concentrations among anatomical sites will be generated at each time point and presented in [Table 24](#) and [Table 25](#). Summaries of IgA antibody concentrations and serum bactericidal antibody (GMT) at each time point and GMFR for other exploratory outcomes are shown starting in [Table 26](#) and concluding with [Table 33](#). Serum Bactericidal Antibody GMT and GMFR will be presented in [Table 34](#).

Summaries of the frequency of antigen-specific immune cells will include the mean if data are reported as percentage, or geometric mean if data are reported as cell count per million cells. The corresponding 95% confidence interval as well as the median, minimum, and maximum values will be presented. Fold rise from baseline will be summarized by arithmetic, geometric mean^[2] or median. The summary of frequencies will be presented starting in [Table 35](#) and concluding with [Table 45](#). Figures depicting the GMT (IgG, IgA) or frequency (MBC, T cells) for each assay over time will be presented beginning with [Figure 10](#) and continuing through [Figure 39](#) (GMTs), and [Figure 74](#) to [Figure 87](#) (frequencies). Reverse cumulative distribution (RCD) plots will be presented with separate panels for each visit, and separate curves within each panel for

each study arm and overall. Antibody titers are shown beginning with **Figure 40** and continuing through **Figure 73**. Percent inhibition of gonococcal adhesion to human cervical cell line (ME180) by mucosal antibodies at day 43 in each treatment group will be show in **Table 46**. The results for each participant at each visit are listed in **Listing 11** through **Listing 22**.

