3.3.2. Immunogenicity Outcomes

In the primary, secondary, and exploratory outcomes, the GMT for Enzyme-Linked Immunosorbent Assay (ELISA) will be calculated for Days 1, 29, 43, 57 and 181 for each treatment arm. The GMT is defined as:

$$GMT = \sqrt[n]{X_1 * X_2 * X_3 * \dots * X_n}$$

In practice, it is the equivalent of: $GMT = \text{Exp}\{[\log(X_1) + \log(X_2) + \dots + \log(X_n)] / n\}$

Where the X_1, X_2, \dots, X_n are the titers for each participant at a certain timepoint. A sample SAS code for calculating the geometric mean and the 95% confidence interval is shown below.

```
proc surveymeans  
  data=data geomean;  
  var variable;  
  run;
```

The geometric mean fold rise (GMFR) for ELISA titers will be calculated for Days 29, 43, 57, and 181 compared to baseline titer in each study arm. The fold change for each participant at each timepoint is calculated first by dividing the follow-up titer by the baseline titer, then the geometric mean and 95% confidence interval will be calculated for each treatment arm at each timepoint.

Similarly, the ratio of serum to mucosal (rectal, vaginal, and oropharyngeal) IgG will be calculated at each time point. The geometric mean and confidence interval will be calculated as above.

Percent inhibition of gonococcal adhesion to human cervical cell line by mucosal antibody is defined as:

$$100\% * [(Titer \text{ without mucosal antibody} - Titer \text{ with mucosal antibody}) / Titer \text{ without mucosal antibody}]$$

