6. GENERAL STATISTICAL CONSIDERATIONS

6.1. General Principles

Unless otherwise specified, continuous variables will be summarized using the following descriptive statistics: n (non-missing sample size), mean, standard deviation, median, minimum and maximum. For some immunogenicity outcomes, the titers /frequencies will be summarized by geometric mean titer (GMT) /geometric mean titer frequencies and confidence interval (CI), fold change (rise or decline) from baseline will be calculated for the follow up immunogenicity outcomes. When calculating geometric mean, only non-zero values will be included. The frequency and percentages (based on the non-missing sample size) of observed levels will be reported for all categorical measures. Exact confidence intervals for binomial proportions will be computed for safety variables. In general, all data will be listed, sorted by Treatment group, and participant, and when appropriate by visit number within participant. All summary tables will be structured with a column for each Treatment in the order presented and will be annotated with the total population size relevant to that table/treatment, including any missing observations.

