[note: The assays may be performed depending on specimen availability and interim immunogenicity analysis report]

Table 32: Oropharyngeal Mucosal IgA against OMV antigens: GMT and GMFR Results Time Point and Treatment Group

Table 33: Oropharyngeal Mucosal IgA against NHBA antigens: GMT and GMFR Results Time Point and Treatment Group

[note: The assays may be performed depending on specimen availability and interim immunogenicity analysis report]

Table 34: Serum Bactericidal antibody GMT and GMFR Results against N. Gonorrhoeae by Time Point and Treatment Group

Table 35: Frequencies of Memory B Cells Specific for OMV and NHBA Antigens by Time Point and Treatment Group

Population	Assay: IgG MBC ELISpot	Statistic	4CMenB				Placebo			
			Day 1	Day 29	Day 43	Day 181	Day 1	Day 29	Day 43	Day 181
Immunogenicity Population	OMV NZ98	N	x	x	x	x	x	x	x	x
		Mean (SD)	x(x)							
		Median (Range)	x(x, x)							
	OMV Ng1291	N	x	x	x	x	x	x	x	x
		Mean (SD)	x(x)							
		Median (Range)	x(x, x)							
	OMV CNG20	N	x	x	x	x	x	x	x	x
		Mean (SD)	x(x)							
		Median (Range)	x(x, x)							
	NHBA NZ98	N	x	x	x	x	x	x	x	x
		Mean (SD)	x(x)							
		Median (Range)	x(x, x)							
	NHBA Ng1291	N	x	x	x	x	x	x	x	x
		Mean (SD)	x(x)							
		Median (Range)	x(x, x)							
	NHBA CNG20	N	x	x	x	x	x	x	x	x
		Mean (SD)	x(x)							
		Median (Range)	x(x, x)							

Table 35: Frequencies of Memory B Cells Specific for OMV and NHBA antigens by Time Point and Treatment Group (continued)

Population	Assay: IgG MBC ELISpot	Statistic	4CMenB				Placebo			
			Day 1	Day 29	Day 43	Day 181	Day 1	Day 29	Day 43	Day 181
Per-protocol Population	OMV NZ98	N	x	x	x	x	x	x	x	x
		Mean (SD)	x(x)							
		Median (Range)	x(x, x)							
	OMV Ng1291	N	x	x	x	x	x	x	x	x
		Mean (SD)	x(x)							
		Median (Range)	x(x, x)							
	OMV CNG20	N	x	x	x	x	x	x	x	x
		Mean (SD)	x(x)							
		Median (Range)	x(x, x)							
Per-protocol Population	NHBA NZ98	N	x	x	x	x	x	x	x	x
		Mean (SD)	x(x)							
		Median (Range)	x(x, x)							
	NHBA Ng1291	N	x	x	x	x	x	x	x	x
		Mean (SD)	x(x)							
		Median (Range)	x(x, x)							
	NHBA CNG20	N	x	x	x	x	x	x	x	x
		Mean (SD)	x(x)							
		Median (Range)	x(x, x)							

Notes: N is the number of participants in each group at given timepoint.
Frequencies are % total IgG-secreting memory B cells (format: 0.00-XXX)

Table 36: Frequencies of Peripheral Blood T Cells Specific for OMV Antigens by Time Point and Treatment Group

Population	Assay: IFNg ELISpot	Statistic	4CMenB							Placebo						

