			Day 1	Day 8	Day 15	Day 29	Day 36	Day 43	Day 57	Day 1	Day 8	Day 15	Day 29	Day 36	Day 43	Day 57
Immunogenicity Population	IFNg NZ98 OMV	N	x	x	x	x	x	x	x	x	x	x	x	x	x	x
		Geometric Mean	x	x	x	x	x	x	x	x	x	x	x	x	x	x
		95% CI	(x, x)	(x, x)	(x, x)	(x, x)	(x, x)	(x, x)	(x, x)							
	IFNg Ng1291 OMV	N	x	x	x	x	x	x	x	x	x	x	x	x	x	x
		Geometric Mean	x	x	x	x	x	x	x	x	x	x	x	x	x	x
		95% CI	(x, x)	(x, x)	(x, x)	(x, x)	(x, x)	(x, x)	(x, x)							
	IFNg CNG20 OMV	N	x	x	x	x	x	x	x	x	x	x	x	x	x	x
		Geometric Mean	x	x	x	x	x	x	x	x	x	x	x	x	x	x
		95% CI	(x, x)	(x, x)	(x, x)	(x, x)	(x, x)	(x, x)	(x, x)							
Per-protocol Population	IFNg NZ98 OMV	N	x	x	x	x	x	x	x	x	x	x	x	x	x	x
		Geometric Mean	x	x	x	x	x	x	x	x	x	x	x	x	x	x
		95% CI	(x, x)	(x, x)	(x, x)	(x, x)	(x, x)	(x, x)	(x, x)							
	IFNg Ng1291 OMV	N	x	x	x	x	x	x	x	x	x	x	x	x	x	x
		Geometric Mean	x	x	x	x	x	x	x	x	x	x	x	x	x	x
		95% CI	(x, x)	(x, x)	(x, x)	(x, x)	(x, x)	(x, x)	(x, x)							
	IFNg CNG20 OMV	N	x	x	x	x	x	x	x	x	x	x	x	x	x	x
		Geometric Mean	x	x	x	x	x	x	x	x	x	x	x	x	x	x
		95% CI	(x, x)	(x, x)	(x, x)	(x, x)	(x, x)	(x, x)	(x, x)							

Note: N is the number of participant in each treatment group at certain timpoint

The frequencies are measured as Spots per million PBMC, format is 0 - xxxx

Table 37: Frequencies of Peripheral Blood T Cells Specific for NHBA Antigens by Time Point and Treatment Group

Population	Assay: IFNg ELISpot	Statistic	4CMenB			Placebo		
			Day 1	Day 15	Day43	Day 1	Day 15	Day43
Immunogenicity Population	NZ98 NHBA Peptide pool	N	x	x	x	x	x	x
		Geometric Mean	x	x	x	x	x	x
		95% CI	(x, x)	(x, x)	(x, x)	(x, x)	(x, x)	(x, x)
	1291 NHBA Peptide pool	N	x	x	x	x	x	x
		Geometric Mean	x	x	x	x	x	x
		95% CI	(x, x)	(x, x)	(x, x)	(x, x)	(x, x)	(x, x)
	CNG20 NHBA Peptide pool	N	x	x	x	x	x	x
		Geometric Mean	x	x	x	x	x	x
		95% CI	(x, x)	(x, x)	(x, x)	(x, x)	(x, x)	(x, x)
Per-Protocol Population	Consensus Peptide pool	N	x	x	x	x	x	x
		Geometric Mean	x	x	x	x	x	x
		95% CI	(x, x)	(x, x)	(x, x)	(x, x)	(x, x)	(x, x)
	NZ98 NHBA Peptide pool	N	x	x	x	x	x	x
		Geometric Mean	x	x	x	x	x	x
		95% CI	(x, x)	(x, x)	(x, x)	(x, x)	(x, x)	(x, x)
	1291 NHBA Peptide pool	N	x	x	x	x	x	x
		Geometric Mean	x	x	x	x	x	x
		95% CI	(x, x)	(x, x)	(x, x)	(x, x)	(x, x)	(x, x)
	CNG20 NHBA Peptide pool	N	x	x	x	x	x	x
		Geometric Mean	x	x	x	x	x	x
		95% CI	(x, x)	(x, x)	(x, x)	(x, x)	(x, x)	(x, x)
	Consensus Peptide pool	N	x	x	x	x	x	x
		Geometric Mean	x	x	x	x	x	x
		95% CI	(x, x)	(x, x)	(x, x)	(x, x)	(x, x)	(x, x)

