	TNFa+ as a % of CD4+	N	x	x	x	x	x	x	x	x	x	x
		Mean (SD)	x(x)	x(x)	x(x)	x(x)	x(x)	x(x)	x(x)	x(x)	x(x)	x(x)
		Median (IQR)	(x, x)	(x, x)	(x, x)	(x, x)	(x, x)	(x, x)	(x, x)	(x, x)	(x, x)	(x, x)
	IFNG+ as a % of CD4+	N	x	x	x	x	x	x	x	x	x	x
		Mean (SD)	x(x)	x(x)	x(x)	x(x)	x(x)	x(x)	x(x)	x(x)	x(x)	x(x)
		Median (IQR)	(x, x)	(x, x)	(x, x)	(x, x)	(x, x)	(x, x)	(x, x)	(x, x)	(x, x)	(x, x)
NHBA CNG20	IL17+ as a % of CD4+	N	x	x	x	x	x	x	x	x	x	x
		Mean (SD)	x(x)	x(x)	x(x)	x(x)	x(x)	x(x)	x(x)	x(x)	x(x)	x(x)
		Median (IQR)	(x, x)	(x, x)	(x, x)	(x, x)	(x, x)	(x, x)	(x, x)	(x, x)	(x, x)	(x, x)
	TNFa+ as a % of CD4+	N	x	x	x	x	x	x	x	x	x	x
		Mean (SD)	x(x)	x(x)	x(x)	x(x)	x(x)	x(x)	x(x)	x(x)	x(x)	x(x)
		Median (IQR)	(x, x)	(x, x)	(x, x)	(x, x)	(x, x)	(x, x)	(x, x)	(x, x)	(x, x)	(x, x)

Table 38: Frequencies of Peripheral Blood CD4+ T Cells Specific for OMV and NHBA Antigens from GC by Time Point and Treatment Group – Intracellular Cytokine Staining (ICS), Immunogenicity Population (continued)

Assay: ICS	Phenotype	Statistic	4CMenB					Placebo				
			Day 1	Day 15	Day 29	Day 43	Day 57	Day 1	Day 15	Day 29	Day 43	Day 57
			N	x	x	x	x	x	x	x	x	x
Consensus peptide pool	IFNG+ as a % of CD4+	Mean (SD)	x(x)	x(x)	x(x)	x(x)	x(x)	x(x)	x(x)	x(x)	x(x)	x(x)
		Median (IQR)	(x, x)	(x, x)	(x, x)	(x, x)	(x, x)					
		N	x	x	x	x	x	x	x	x	x	x
Consensus peptide pool	IL17+ as a % of CD4+	Mean (SD)	x(x)	x(x)	x(x)	x(x)	x(x)	x(x)	x(x)	x(x)	x(x)	x(x)
		Median (IQR)	(x, x)	(x, x)	(x, x)	(x, x)	(x, x)					
		N	x	x	x	x	x	x	x	x	x	x
Consensus peptide pool	TNFa+ as a % of CD4+	Mean (SD)	x(x)	x(x)	x(x)	x(x)	x(x)	x(x)	x(x)	x(x)	x(x)	x(x)
		Median (IQR)	(x, x)	(x, x)	(x, x)	(x, x)	(x, x)					
		N	x	x	x	x	x	x	x	x	x	x
Consensus peptide pool	IFNG+ as a % of CD4+	Mean (SD)	x(x)	x(x)	x(x)	x(x)	x(x)	x(x)	x(x)	x(x)	x(x)	x(x)
		Median (IQR)	(x, x)	(x, x)	(x, x)	(x, x)	(x, x)					
		N	x	x	x	x	x	x	x	x	x	x

Note: Frequencies are presented as percentage format 0.00% - 99.99%

[Implementation note for above and below table, the values reported in the table are values derived from (original value - background value)]

Same format for the following tables:

Table 39: Frequencies and Function of Peripheral Blood CD4+ T cells Specific for Antigens by Time Point and Treatment Group - ICS - Per-Protocol Population**Table 40: Frequencies and Function of Peripheral Blood CD8+ T cells Specific for Antigens by Time Point and Treatment Group - ICS - Immunogenicity Population**

[note: The CD8 table should not contain IL17+ as cytokine]

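### SAP 8.3 permits an arithmetic mean of cell-frequency fold rises, which lies above 1 in expectation when nothing changed, and applies a ratio to background-subtracted ICS values that can sit at or near zero

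*SAP*

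**What the plan says.** SAP 8.3 treats the cell frequencies and their fold rise in separate sentences. The summary of the frequencies "will include the mean if data are reported as percentage, or geometric mean if data are reported as cell count per million cells". For the change over time it says "Fold rise from baseline will be summarized by arithmetic, geometric mean" or median, and gives no rule for choosing. SAP 6.1 also calls for fold change from baseline on follow-up immunogenicity outcomes.

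The only definition of fold change is in SAP 3.3.2: "The fold change for each participant at each timepoint is calculated first by dividing the follow-up titer by the baseline titer". It is written for ELISA titers, and there the summary is the geometric mean with a 95% CI.

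The table shells (SAP Appendix 1) describe the data:

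- **ICS percentages, Table 38 for peripheral blood and Table 42 for rectal tissue, with the tables sharing their formats:** an implementation note says "the values reported in the table are values derived from (original value - background value"). The footnote reads "Frequencies are presented as percentage format 0.00% - 99.99"%. No floor is stated for negative differences.
- **T-cell ELISpot, Tables 36 and 37:** "The frequencies are measured as Spots per million PBMC, format is 0 - xxxx".
- **Memory B-cell ELISpot, Table 35:** "Frequencies are % total IgG-secreting memory B cells", in a format that starts at 0.00.

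The only rule for zeros is in SAP 6.1: "When calculating geometric mean, only non-zero values will be included". Nothing covers zeros under an arithmetic mean or median, a zero baseline, or a negative value. None of the shells for Tables 35 to 45 has a fold-rise row.

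**The concern.** A fold rise is read against 1. A summary that sits above 1 in expectation when nothing has happened invites the reader to see a response, in the placebo arm as well as the vaccine arm. If the spread of the ratios or the arm size differs between arms, the comparison of arms is affected too.

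The second difficulty is separate and belongs to the ratio, not to the average taken of it. Subtracting background can leave a baseline at zero, just above zero or below zero. Division by such a value gives no number, a very large number, or a number with the wrong sign or direction.

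The SAP sets out to characterise B-cell and T-cell responses compared with placebo and plans no hypothesis test, so these descriptive figures would carry the interpretation. The ELISA analyses, including the primary and secondary antibody outcomes, use the geometric mean fold rise and are not touched.

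**Working it through.** The plan states no figure on this point, so there is nothing to reproduce. The inputs are the fold-change definition (SAP 3.3.2), the permitted summaries (SAP 8.3), the data formats (Tables 35 to 45) and the arm sizes: 40 and 10 overall, 16 and 4 in the biopsy cohort. The SD of the log fold change and the noise of background-subtracted ICS values are not in the documents. Both are assumed below, over a range.

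**1. Arithmetic mean of positive ratios, no true change.** Let R be follow-up divided by baseline. If the two values are exchangeable, R and 1/R have the same distribution, so E[R] = E[(R + 1/R)/2] ≥ 1.

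- Two participants, one doubling and one halving: arithmetic mean (2 + 0.5)/2 = 1.25; geometric mean √(2 × 0.5) = 1.00.
- Log-normal R with median 1 and log SD s: E[R] = exp(s²/2). For s = 0.5, 0.7 and 1.0 this is exp(0.125) = 1.13, exp(0.245) = 1.28 and exp(0.5) = 1.65. At s = 0.3 it is 1.05 and at s = 1.5 it is 3.08. The true geometric mean and median are 1.00 throughout.

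This is a statement about the expectation. The chance that an observed mean exceeds 1 under no change, from 100,000 simulated arms per setting, is:

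| Arm size | Arithmetic, s = 0.5 | Arithmetic, s = 1.0 | Geometric, either s |
|---|---|---|---|
| 40 | 0.93 | 0.99 | 0.50 |
| 16 | 0.81 | 0.94 | 0.50 |
| 10 | 0.75 | 0.87 | 0.50 |
| 4 | 0.64 | 0.72 | 0.50 |

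**2. Ratios of background-subtracted values.** Examples in percentage points:

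- Baseline 0: the ratio is undefined.
- Baseline −0.02, follow-up 0.10 (a rise): 0.10/−0.02 = −5.0.
- Baseline −0.05, follow-up −0.01 (a rise): 0.2, which reads as a fall.
- Baseline 0.05, follow-up −0.01: −0.2.

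A geometric mean cannot take a ratio at or below zero, and a median of such ratios is distorted.

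**3. How often a baseline is at or below zero.** Take a true net value m and normal noise SD e, rounded to 0.01% as in the shell format. A baseline then shows as zero or less with probability Φ((0.005 − m)/e). All values of m and e are assumed.

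- m = 0.10, e = 0.03: Φ(−3.17), about 0.1%.
- m = 0.05, e = 0.03: Φ(−1.5) = 6.7%. The chance of at least one in an arm is 1 − 0.933^n: 0.50 for n = 10, 0.67 for n = 16 and 0.94 for n = 40.
- m = 0.05, e = 0.05: Φ(−0.9) = 18%. Here, with zero baselines dropped and negatives kept, the arithmetic mean fold rise at n = 10 was itself negative in 18% of simulated arms.

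The frequency therefore runs from negligible to common, depending on assay noise that the documents do not report.

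**The case against.** The strongest reply is that little hangs on this. The outcomes are exploratory and descriptive, no shell for Tables 35 to 45 displays a fold rise, and participant-level values are listed. The upward bias arises in both arms, and the objectives are read against placebo. All of that stands and limits the weight of the point. It does not remove it: SAP 6.1 and 8.3 both commit to the calculation, and one of the three permitted statistics is biased.

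Several stronger readings are tempting, and the documents do not support them:

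- A reader might infer that the arithmetic mean always shows a rise. It does so only in expectation; ratios of 0.5 and 0.6 average 0.55.
- A reader might infer that reported ICS fold rises will change sign. That requires negative values to be kept. The format starting at 0.00% may mean they are set to zero, which the SAP does not state; sign changes would then become undefined ratios.
- A reader might infer that the mean is assigned to the fold rise of percentage data. That rule in SAP 8.3 covers the frequencies only.
- A reader might infer that one near-zero baseline will dominate a mean among the 4 placebo participants with biopsies. The rectal shell (Table 42) shows median, IQR and range but no mean, and its assays are conditional on specimens and the interim report.
- A reader might infer that the open choice allows the most favourable figure to be picked. Nothing in the documents indicates that intent.
- A reader might take Protocol Table 2 as evidence for s. Its intervals imply log SDs from 0.485 to 1.141, but these are between-person SDs of serum titers at one time, not SDs of within-person ratios of cell frequencies. Even if the placebo Ng OMV value of 0.689 is borrowed, the expected mean is exp(0.689² × (1 − ρ)): 1.61, 1.27 or 1.10 for within-person correlation ρ of 0, 0.5 or 0.8, and ρ is not given.

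**Conclusion.** The point holds in two parts. The arithmetic mean of individual fold rises is biased upward in expectation under no change, by 13% to 65% for an assumed log SD of 0.5 to 1.0 with positive values. Separately, no fold-rise summary suits background-subtracted ICS percentages, because a baseline at or near zero makes the ratio undefined or unstable and a negative one, if retained, misstates its sign or direction. Changing from one average to another repairs the first part only. How often the second part would bite cannot be settled from the documents. This is a minor but concrete improvement to exploratory analyses; it does not bear on the primary or secondary results.

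**What to change.** In SAP 8.3, delete the arithmetic option and name one summary per assay:

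- **T-cell ELISpot counts:** geometric mean fold rise with 95% CI, and one stated rule for zero values, applied to baseline and follow-up alike. Leaving it to SAP 6.1, which omits zeros from geometric means, would discard participants who move to or from zero.
- **Background-subtracted ICS percentages:** replace fold rise with change from baseline in percentage points (median, IQR).
- **Memory B-cell percentages, which can also be zero:** the same percentage-point change.

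Adjust the general fold-change sentence in SAP 6.1 to match. If these results are to be tabulated, add a row to the shells.

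The cost is a few sentences of SAP text and no new data. The downside is that ICS and memory B-cell results would no longer be on the fold scale used for antibodies.

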9. SAFETY EVALUATION

All summaries and analysis of safety data will be presented for the safety analysis population. Safety summaries will be presented overall and stratified by treatment group. Listings will be sorted by treatment group, participant ID, parameter (if applicable), and visit. Continuous variables will be summarized using the following descriptive statistics: n (non-missing sample size), mean, standard deviation, median, maximum and minimum. All categorical measures will be summarized by the frequency and percentages (based on the non-missing sample size) of observed levels.

9.1. Demographic and Other Baseline Characteristics

Summaries of age, sex, ethnicity, and race will be presented by treatment group overall for all enrolled participants ([Table 11](#) and [Table 12](#)). Ethnicity is categorized as Hispanic or Latino, or not Hispanic and not Latino. In accordance with NIH reporting policy, participants may self-designate as belonging to more than one race or may refuse to identify a race, the latter reflected in the CRF as “No” to each racial option. Individual participant listings will be presented for all demographics ([Listing 6](#)). Sexual history at baseline will be presented ([Table 47](#) and [Table 48](#)). Sexual history during follow-up visits will be presented ([Table 49](#) and [Table 50](#)).

9.1.1. Pre-Existing Medical Conditions

All current illnesses and past pre-existing medical conditions will be MedDRA® coded using MedDRA dictionary version 21.1 or higher. Summaries of all enrolled participants’ pre-existing medical conditions will be presented by treatment group ([Table 13](#)). Individual participant listings will be presented for all medical conditions ([Listing 7](#)).

